7.5 Registration, Randomization and Blinding

Registration will occur following verification of eligibility by the treating physician.

Participants who are consented and accrued to the study should be registered in OnCore in accordance with the Clinical Trial Management System Policy via the UVa OnCore Resources link in Oncore. General guidelines are available in the OnCore User Manual and Data Entry Guide.

Treatment allocation will be discussed with participants during the process of informed consent, and informed consent must be documented prior to randomization. The study participants will be randomized to either the treatment group or placebo group (1:1 ratio) once consent is signed and inclusion/exclusion criteria are satisfied. All investigators and subjects will be blinded. The study coordinator will have the master randomization list.

7.5.1 Emergency Unblinding Procedures

Randomization codes and corresponding treatment assignment will be made available to the Primary Investigator (PI) for emergency use when applicable. If it is not reasonable to inform the PI in advance of unblinding, the study staff must promptly document in the subject's source record and should subsequently contact the PI to explain any premature unblinding of treatment assignment [such as accidental unblinding or unblinding due to a serious adverse event (SAE)]. The PI will document within study correspondence the rationale, circumstances, and the person or persons being informed about the unblinding.

7.6 Concomitant Therapy

For this protocol, a prescription medication is defined as a medication that can be prescribed only by a properly authorized/licensed clinician. Medications to be reported in the Case Report Form (CRF) are concomitant prescription medications, over-the-counter medications and supplements.

8 STUDY CLOSURE, STUDY INTERVENTION DISCONTINUATION AND PARTICIPANT DISCONTINUATION OR WITHDRAWAL

8.1 Study Discontinuation and Closure

This study may be temporarily suspended or prematurely terminated if there is sufficient reasonable cause. Written notification, documenting the reason for study suspension or termination, will be provided by the suspending or terminating party to the investigator, the Investigational New Drug (IND) sponsor and regulatory authorities. If the study is prematurely terminated or suspended, the Principal Investigator (PI) will promptly inform the Institutional Review Board (IRB) and will provide the reason(s) for the termination or suspension. Study participants will be contacted, as applicable, and be informed of changes to study visit schedule.

Circumstances that would warrant termination or suspension include, but are not limited to

- Determination of unexpected, significant, or unacceptable risk to participants
- Demonstration of efficacy that would warrant stopping
- Insufficient compliance to protocol requirements
- Data that are not sufficiently complete and/or evaluable
- Determination that the primary endpoint has been met
- Determination of futility
- Change in funding status

Study may resume once concerns about safety, protocol compliance, and data quality are addressed by the IRB, and Food and Drug Administration (FDA).

Participants receiving study treatment at the time of study discontinuation should complete procedures described in section 8.3.

8.2 Participant Discontinuation/Withdrawal

Participants are free to withdraw from participation in the study at any time upon request.

A participant's study treatment would be discontinued for the following reasons:

- Significant study intervention non-compliance
- If any clinical adverse event (AE), laboratory abnormality, or other medical condition or situation occurs such that continued participation in the study would not be in the best interest of the participant
- Disease progression which requires discontinuation of the study intervention
- If the participant meets an exclusion criterion (either newly developed or not previously recognized) that precludes further study participation
- Participant decision to withdraw from study treatment and/or the study.

The reason for participant discontinuation or withdrawal from study treatment will be recorded. Participants who sign the informed consent form and are randomized but do not receive the study intervention may be replaced. Participants who sign the informed consent form, and are randomized and receive the study intervention, and subsequently withdraw, or are withdrawn or discontinued from the study, will not be replaced.

Participants that withdraw from the study (not only from study treatment, but all study follow-up) will not be contacted for any further study visits.

8.3 Procedures for Discontinuation of Study Intervention

Discontinuation from study treatment means that the subject is withdrawn from the study. In the event of study discontinuation, the participant will not be contacted for any further study visits.

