
To determine the safety of treatment CBD.
	
Safety will be determined by evaluating:
 
 • The frequency and severity of adverse events from the beginning of treatment through the end of study participation. • Changes in skin appearance from baseline using standardized skin assessment tool. (patient will be removed from study with a score ≥ 2) • Clinically significant change in CBC (baseline and follow-up) • Clinically significant change in basic metabolic panel (i.e., BUN, creatinine, CO₂, Cl, K, Na, and glucose) (baseline and weekly follow-up) • Clinically significant change in hepatic function testing (i.e., serum transaminases [ALT/AST], total bilirubin, and alkaline phosphatase) (baseline and weekly follow-up) • Clinically significant change in vital sign assessments (i.e., heart rate and blood pressure) (baseline and weekly follow-up) • Suicidal behavior and thoughts as a specific question using the Columbia-Suicide Severity Rating Scale (C-SSRS) (baseline and weekly follow-up)
--	--

Study Population: 40 subjects with presenting with thumb basal joint arthritis over the age of 18 will be recruited from the UVA Hand Center.

Description of Sites/Facilities This will be a single-site study conducted at the UVA Hand Center at the University of Virginia.

Enrolling**Participants:****Description of****Study****Intervention:**

[figure not shown]
The study design will be a double-blind randomized control trial with crossover. Treatment will be blinded to the subjects and investigators. Patients will be randomly assigned two (2) weeks of the case (CBD) or control cream and then crossover to the other cream for two (2) additional weeks. Patients will apply the topical cream at their thumb basal joint twice daily for 1 hour. The subjects will be advised to observe for physiologic changes, skin changes, or other adverse effects. If mild to serious adverse events are noticed, the creams will be removed immediately and appropriate care and observation will be taken. Each condition will last for 2 weeks and then subjects will be contacted by the study coordinator to facilitate crossover into the other condition. To capture any delayed-onset adverse events, including those related to skin changes that might develop after the drug is discontinued, subjects will attend a follow-up visit seven (7) days following the last dose of investigational cream.

Study**Duration:****Participant****Duration:**

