4 OBJECTIVES AND ENDPOINTS

Objectives	Endpoints
Primary	
To determine therapeutic potential of CDB as a topical	Hand Functional Assessment: Change from baseline in hand functional assessment including grip, appositional,

treatment for thumb basal joint arthritis.	
and oppositional pinch strength (kg); Kapandji score; and MP and IP range of motion.
 
Patient Reported Outcome Measures: Change from baseline in the PROMIS-29 (Patient-Reported Outcomes Measurement Information System) and PROMIS upper extremity tests. The PROMIS-29 is a free publicly available generic health related quality of life (HRQoL) measure consisting of indices of pain, pain interference, depression, anxiety, global function, and social interactions. The PROMIS upper extremity test utilizes item-response theory and Computer Adaptive Test to efficiently and precisely report patient symptoms and perceived function.

Secondary	
To determine the safety of treatment CBD.
 
Safety will be determined by evaluating:
 
 • The frequency and severity of adverse events from the beginning of treatment through the end of study participation. • Changes in skin appearance from baseline using standardized skin assessment tool (patient will be removed from study with a score ≥ 2) • Clinically significant change in CBC (baseline and weekly follow-up) • Clinically significant change in basic metabolic panel (i.e., BUN, creatinine, CO₂, Cl, K, Na, and glucose) (baseline and weekly follow-up) • Clinically significant change in hepatic function testing (i.e., serum transaminases [ALT/AST], total bilirubin, and alkaline phosphatase) (baseline and weekly follow-up) • Clinically significant change in vital sign assessments (i.e., heart rate and blood pressure) • Suicidal behavior and thoughts as a specific question using the Columbia-Suicide Severity Rating Scale (C-SSRS) at baseline and follow-up.

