5 STUDY DESIGN

5.1 Overall Design

The study design will be a double-blind randomized controlled trial with crossover. Treatment will be blinded to the subjects and investigators. Patients will be randomly

assigned two (2) weeks of the case or control topical cream and then crossover to the other cream for two (2) more weeks. Patients will apply the cream at their thumb basal joint twice daily for one (1) hour. The subjects will be advised to observe for physiologic changes, skin changes, or other adverse effects. If mild to severe drug-related adverse events are noticed, the creams will be removed immediately and appropriate care and observation will be taken. Each condition will last for two (2) weeks and then subjects will be contacted by the study coordinator to facilitate crossover into the other condition. This study will last one year from the beginning of subject recruitment to data analysis. Subjects will be enrolled in this study for approximately six (6) weeks from Screening until the final Study Visit.

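### Section 8.3 turns stopping the cream into study withdrawal, which conflicts with the safety visit the synopsis sets 7 days after the last dose

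*Combined protocol and SAP*

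**What the plan says.** Section 8.3 has two sentences. The first is "Discontinuation from study treatment means that the subject is withdrawn from the study". The second is "In the event of study discontinuation, the participant will not be contacted for any further study visits".

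Section 8.2 lists adverse events and laboratory abnormalities among the reasons for stopping treatment. Its own no-contact rule is limited to subjects who leave all follow-up, and it sets them apart from subjects who leave treatment only. Section 9.2 removes from the study any subject with a skin score of 2 or more.

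The synopsis (section 1.1) gives a purpose, "To capture any delayed-onset adverse events, including those related to skin changes that might develop after the drug is discontinued", and a measure to serve it: "subjects will attend a follow-up visit seven (7) days following the last dose of investigational cream". The amendment history (section 14.2) records the addition of this visit as a response to an FDA clinical hold. The Schedule of Activities (section 14.1) shows it once, as Visit 7 on Day 35, and has no early-termination column.

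Three other provisions matter:
- Section 4 defines the adverse event endpoint as "The frequency and severity of adverse events from the beginning of treatment through the end of study participation".
- Section 10.1.4 requires documentation of events that arise while the subject is on study, and follow-up of all events until they resolve. Section 5.1 adds that when a drug-related event is noticed, "the creams will be removed immediately and appropriate care and observation will be taken".
- Section 8.1 covers a study-wide stop. Participants are to be contacted, where applicable, about changes to their visits, and those on cream are referred to the procedures in 8.3.

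**The concern.** Safety is the trial's secondary objective, and the post-dose visit exists to find events that appear after the cream is stopped. A subject taken off the cream because of harm is someone for whom that visit has an obvious use. Under 8.3 it would not be held for that subject, while a subject who completes both periods without trouble would have it.

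The protocol therefore gives site staff two rules that cannot both be followed. One ties a visit to the last dose. The other ends participation when dosing ends. The second is the specific rule for early stoppers, so it is the one staff are likely to apply. A new reaction that begins after the stop would then be found only if the subject reported it unprompted, or if it came to light during follow-up of an event already known.

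**Working it through.** The protocol states no figure on this point, so the check sets its provisions side by side and then counts from the schedule.

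**1. What each provision does for a subject who stops early and has not refused follow-up**

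| Provision | Effect |
|---|---|
| 8.3, first sentence | Withdraws the subject from the study |
| 8.3, second sentence | No further visits, if study discontinuation here means the subject's own; it could instead mean closure of the whole study, the sense used in 8.1 |
| 8.2 | No contact only for those who leave all follow-up; treatment-only stopping is a separate state, which 8.3 then removes |
| Synopsis | A visit 7 days after the last dose; read alone, this can include early stoppers |
| 14.1 | Visit 7 at Day 35 only |
| 10.1.4 and 5.1 | Known events followed, with care and observation; no visit or timing for finding new ones |

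The ambiguity in the second sentence of 8.3 does not rescue the early stopper, because the first sentence has already withdrawn the subject. The result is a conflict between 8.3 on one side and the synopsis and 8.2 on the other.

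**2. Which events fall outside.** If participation ends at the stop, an event that starts later is neither on study (10.1.4) nor inside the endpoint window (section 4). An event known before the stop is inside both, and its changes in severity and its resolution are still recorded.

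**3. What Visit 7 contains.** Rows marked at Visit 7 in section 14.1: blood draw, physician skin score, C-SSRS, somnolence and sedation check, diary review, adverse event assessment. Total = 6.

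**4. Timing, on nominal days.** A completer's last dose is at about Day 28, and 35 - 28 = 7 days off treatment. Take stops at Days 7, 14 and 21:

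| Stop | Scheduled off-treatment days under 8.3 | Post-dose visit if held | Off-treatment days if held |
|---|---|---|---|
| Day 7 | 0 | 7 + 7 = Day 14 | 7 |
| Day 14 | 0 | 14 + 7 = Day 21 | 7 |
| Day 21 | 0 | 21 + 7 = Day 28 | 7 |

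A stop at Day 7, 14 or 21 also means that 4, 3 or 2 of the 5 post-baseline visits are not held. Most of those are on-treatment visits that end because the cream ends. The recoverable part is one visit and 7 days in each case.

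**5. Bloods.** Under sections 9.2 and 14.1 the only post-baseline draw is at Day 35, so an early stopper has 0 of 1. The endpoint tables mention weekly testing for some panels. On that reading there are 5 planned draws (Days 7 to 35), and a stop at Day 7, 14 or 21 leaves at most 1, 2 or 3 of them. None falls about 7 days after the last dose. The post-dose draw is lost on either reading.

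**6. Scale.** Each early stopper is 1/40 = 2.5% of the planned sample. The documents give no stopping rate and no rate of delayed events. Purely as an assumption, 5% to 20% stopping early would be 0.05 x 40 = 2 to 0.20 x 40 = 8 subjects.

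**The case against.** The strongest defence is that the synopsis already covers early stoppers. It counts from the last dose, not from Day 35, and its stated purpose is events after the drug is discontinued. That reading is available, so a reader who infers that the protocol nowhere provides such a visit goes too far. What remains is a specific rule in 8.3 that points the other way, and a schedule that shows the visit only at Day 35.

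A reader might also infer that observation of a harmed subject simply ends at the stop. The documents do not support this. A subject removed for a skin score or an adverse event has a known event, which 10.1.4 follows until it resolves, including any worsening, and 5.1 requires care and observation. For the same reason, the missing visit does not prevent a judgement on dechallenge under section 10.1.3.2. Nor should the point be extended to every mild event: removal of the cream in 5.1 may mean only taking it off the skin.

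For a study-wide stop, including one for "Determination of unexpected, significant, or unacceptable risk to participants", it is tempting to say that subjects are left without contact. Section 8.1 says otherwise, since it provides for contact where applicable. It does not guarantee a post-dose visit, however, and the section it refers to contains no procedure for one.

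Finally, section 3.1.1 reports no major side effects in earlier topical studies, and the number of affected subjects is unknown. Both are fair reasons not to overstate the point. Neither is a reason to leave two conflicting rules in place.

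**Conclusion.** The concern holds as a conflict of rules. Section 8.3, read with 8.2, ends scheduled visits when the cream stops. The synopsis sets a visit 7 days after the last dose, and 8.2 recognises a subject who leaves treatment but not follow-up. Following 8.3 loses scheduled detection of new events that begin after the stop, together with the post-dose assessments.

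The size is one visit, six assessments and 7 days of off-treatment observation per early stopper. This rests on nominal visit days and on the natural reading of 8.3. Neither the total loss nor any bias can be estimated from the documents. A biased laboratory comparison between creams should not be inferred: in completers the Day 35 draw follows both creams, so the issue is detection and follow-up in the individual subject.

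The point should be fixed because the subjects affected include those stopped for harm, and the remedy is small.

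**What to change.** Leave every rule on when the cream stops unchanged. Rewrite section 8.3 to say:

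- Any subject who stops the cream, including by removal for a skin score of 2 or more or because of a study-wide stop, and who has not withdrawn from all follow-up, attends the Visit 7 assessments 7 (+/- 1) days after the last application.
- New adverse events found at that visit are recorded as on-study. Events already open continue to be followed under 10.1.4.
- The rule of no further visits applies only to subjects who withdraw from all follow-up, as in 8.2.

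This also gives the cross-reference in 8.1 a procedure to point to. The cost is one paragraph in an amendment and, per early stopper, one already-planned visit moved to an earlier date. It recovers nothing for subjects who decline all follow-up.

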8.4 Lost to Follow-Up

A participant will be considered lost to follow-up if he or she fails to return for one scheduled visit and is unable to be contacted by the study site staff.

The following actions must be taken if a participant fails to return to the clinic for a required study visit:

- The site will attempt to contact the participant and reschedule the missed visit within 24 hours and counsel the participant on the importance of maintaining the assigned visit schedule and ascertain if the participant wishes to and/or should continue in the study.
- Before a participant is deemed lost to follow-up, the investigator or designee will make every effort to regain contact with the participant.
- These contact attempts should be documented in the study file.
- Should the participant continue to be unreachable, he or she will be considered to have withdrawn from the study with a primary reason of lost to follow-up.

9 STUDY ASSESSMENTS AND PROCEDURES

9.1 Clinical Assessments

Hand Functional Assessment: Hand functional assessment will include grip, appositional, and oppositional pinch strength (kg); Kapandji score; and MP and IP range of motion. Assessments will be performed at Baseline and study Days 7, 14, 21, and 28.

Patient Reported Outcome Measures: The PROMIS-29 and PROMIS upper extremity tests will be collected. The PROMIS-29 is a free publicly available generic HRQoL measure consisting of indices of pain, pain interference, depression, anxiety, global function, and social interactions (Attachment 1, Appendix 14.4) Subjects will complete the measure at Baseline and study Days 7, 14, 21, and 28. The PROMIS upper extremity test utilizes item-response theory and Computer Adaptive Test to efficiently and precisely report patient symptoms and perceived function. Subjects will complete the measure in clinic using an iPad. The PROMIS upper extremity assessment is provided in Attachment 2 (Appendix 14.4). Subjects will complete the PROMIS assessment at Baseline and study Days 7, 14, 21, and 28.

9.2 Safety Assessments

Medical History: Relevant medical history, including history of mental illness, drug or substance abuse, history of hemp-based product usage and other pertinent history will be recorded in the case report form.

Laboratory Testing: At baseline and Study Day 35, blood draws will be performed on all subjects at the UVA Medical Laboratory. The following tests will be ordered and monitored for clinical abnormalities:

- CBC
- Basic metabolic panel (i.e., BUN, creatinine, CO₂, Cl, K, Na, and glucose)
- Hepatic function testing (i.e., serum transaminases [ALT/AST], total bilirubin, and alkaline phosphatase)
- Pregnancy Testing (if applicable) (Screening)
- Urine Pregnancy Test (if applicable) (Screening and Day 0 before dosing)

Daily Skin Monitoring: Subjects will be asked to observe the testing site for physiologic changes, skin changes or other adverse events daily. Subjects will be provided with a daily diary to record and monitor any observed changes. The daily diary is provided in Appendix 14.3. They will be instructed to notify the investigator of any sudden changes in skin appearance or increase in their arthritic symptoms that are more than minimally tolerated.

Physician Skin Monitoring: At baseline and at every subsequent visit, the investigator will assess the CBD cream site for adverse events. A score will be given corresponding to the assessment tool below:

Score	Definition
0	No erythema
1	Minimal erythema
2	Moderate erythema with sharply defined borders
3	Intense erythema with or without edema
4	Intense erythema with edema and blistering/erosion

- NOTE: Changes in skin appearance will be evaluated using the standardized skin assessment tool above. A patient will be removed from study with a score ≥ 2 .

Clinical Evaluations: Subjects will be monitored weekly for the following:

- Vital sign assessments (i.e., heart rate and blood pressure)
- Suicidal behavior and thoughts as a specific question using the Columbia-Suicide Severity Rating Scale (C-SSRS). The full questionnaire is provided in Attachment 3 (Appendix 14.4).
 - Monitor for somnolence and sedation and advise patients not to drive or operate machinery until they have gained sufficient experience on study drug. Subjects will be asked if they feel more, less, or no change in their level of fatigue during the time they were administering study drug.

Adverse Event Monitoring: Information regarding occurrence of adverse events will be captured throughout the study. Duration (start and stop dates and times), severity/grade, outcome, treatment and relation to study intervention will be recorded.

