10.1.3.2 Relationship to Study Intervention

All AEs must have their relationship to study intervention assessed by the clinician who examines and evaluates the participant based on temporal relationship and his/her clinical judgment. The degree of certainty about causality will be graded using the categories below. In a clinical trial, the study product must always be suspect.

- **Definitely Related** – There is clear evidence to suggest a causal relationship, and other possible contributing factors can be ruled out. The clinical event, including an abnormal laboratory test result, occurs in a plausible time relationship to study intervention administration and cannot be explained by concurrent disease or other drugs or chemicals.
- **Probably Related** – There is evidence to suggest a causal relationship, and the influence of other factors is unlikely. The clinical event, including an abnormal laboratory test result, occurs within a reasonable time after administration of the study intervention, is unlikely to be attributed to concurrent disease or other

drugs or chemicals, and follows a clinically reasonable response on withdrawal (dechallenge).

- **Possibly Related** – There is some evidence to suggest a causal relationship (e.g., the event occurred within a reasonable time after administration of the trial medication). However, other factors may have contributed to the event (e.g., the participant's clinical condition, other concomitant events). Although an AE may rate only as "possibly related" soon after discovery, it can be flagged as requiring more information and later be upgraded to "probably related" or "definitely related", as appropriate.
- **Unlikely to be related** – A clinical event, including an abnormal laboratory test result, whose temporal relationship to study intervention administration makes a causal relationship improbable (e.g., the event did not occur within a reasonable time after administration of the study intervention) and in which other drugs or chemicals or underlying disease provides plausible explanations (e.g., the participant's clinical condition, other concomitant treatments).
- **Not Related** – The AE is completely independent of study intervention administration, and/or evidence exists that the event is definitely related to another etiology. There must be an alternative, definitive etiology documented by the clinician.

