10.1.4 Time Period and Frequency for Event Assessment and Follow-Up

The occurrence of an AE or SAE may come to the attention of study personnel during study visits and interviews of a study participant presenting for medical care.

All AEs including local and systemic reactions not meeting the criteria for SAEs will be captured on the appropriate case report form (CRF). Information to be collected includes event description, time of onset, clinician's assessment of severity, relationship to study product (assessed only by those with the training and authority to make a diagnosis), and time of resolution/stabilization of the event. All AEs occurring while on study must be documented appropriately regardless of relationship. All AEs will be followed to adequate resolution.

Any medical condition (including a laboratory abnormality) that is present at the time that the participant is screened will be considered as baseline and not reported as an AE. However, if the study participant's condition deteriorates at any time during the study, it will be recorded as an AE.

Changes in the severity of an AE will be documented to allow an assessment of the duration of the event at each level of severity to be performed. AEs characterized as intermittent require documentation of onset and duration of each episode.

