14 APPENDICES

14.1 Schedule of Activities (SoA)

Visit	Visit 1 (Screening and Baseline)	Visit 2 (Baseline)	Visit 3	Visit 4	Visit 5	Visit 6	Visit 7
Study Day	-7 ¹	0	7 (+/- 1)	14 (+/- 1)	21 (+/- 1)	28 (+/- 1)	35 (+/- 1)
Informed Consent	X						
Review study eligibility	X						
Blood Draw ²	X ³						X
Urine Pregnancy Test (if applicable)	X	X					
Hand Functional Assessment		X	X	X	X	X	
Patient Reported Outcome Measures		X	X	X	X	X	
Physician Skin Monitoring		X	X	X	X	X	X
Columbia- Suicide Severity Rating Scale	X	X	X	X	X	X	X

¹ Screening may take place within one week of baseline visit to allow for results of bloodwork and pregnancy testing.

² Blood pregnancy test to be ordered during screening visit only.

³ Baseline blood testing (Hemoglobin and Platelet count, Creatinine, AST/ALT) will be obtained at the screening blood draw.

Monitor for somnolence and sedation			X	X	X	X	X
Study Medication Dispensed		X		X			
Diary dispensed		X		X			
Diary Review			X	X	X	X	X
Study Medication Collected			X	X	X	X	
Assessment of Adverse Events		X	X	X	X	X	X

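### Sections 1.1 and 4 call for weekly laboratory safety endpoints, but no laboratory test is scheduled on either cream; the only post-baseline draw is at Day 35, nominally 7 or 21 days after the last CBD dose

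*Combined protocol and SAP*

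**What the plan says.** **Endpoint tables.** Section 4 gives a weekly frequency for all three laboratory panels; for the blood count the entry reads "Clinically significant change in CBC (baseline and weekly follow-up". The synopsis (Section 1.1) differs on the blood count, "Clinically significant change in CBC (baseline and follow-up", but keeps weekly testing for the metabolic and hepatic panels, the latter as "i.e., serum transaminases [ALT/AST], total bilirubin, and alkaline phosphatase) (baseline and weekly follow-up".

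**Operational sections.** Section 9.2 provides two draws: "At baseline and Study Day 35, blood draws will be performed on all subjects at the UVA Medical Laboratory". The schedule of activities (Section 14.1) marks blood draws at Visit 1 (Day -7) and Visit 7 (Day 35) only. Its footnotes make the screening sample the baseline, "Baseline blood testing (Hemoglobin and Platelet count, Creatinine, AST/ALT) will be obtained at the screening blood draw", and allow some freedom in its timing: "Screening may take place within one week of baseline visit to allow for results of bloodwork and pregnancy testing".

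**Treatment timing.** Each cream is used for two weeks (Section 5.1), nominally Days 0 to 14 and 14 to 28. The second supply is dispensed at Day 14, and no washout is scheduled.

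**Stopping early.** Section 8.3 treats stopping the cream as withdrawal from the study, and says that after study discontinuation the participant is not contacted for more visits. Section 8.2 separates leaving treatment from leaving all follow-up. The synopsis places a safety visit 7 days after the last dose.

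**The concern.** The endpoint tables promise data that the operational sections do not collect. A site that follows Section 9.2 and the schedule obtains one baseline-to-Day-35 change per subject, measured after both creams have been stopped. Samples not taken during treatment cannot be recovered later.

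Two losses follow. A change in liver enzymes, chemistry or blood count that appears on cream and has resolved by Day 35 is invisible to scheduled testing. An abnormality first seen at Day 35 could have begun before dosing, on CBD, on control or in the week after treatment. Section 8.2 also names a laboratory abnormality as a possible reason to stop treatment; on the present schedule only an unscheduled test could reveal one during treatment.

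The secondary worry is that subjects removed for an adverse event, or for a skin score of 2 or more, may not reach even the Day 35 draw if Section 8.3 is read to end their visits.

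**Working it through.** **Inputs.** Visit days and ±1-day windows for Days 14, 28 and 35, and screening at Day -7 (Section 14.1); two weeks per cream (Section 5.1); 28 mL per supply at 1 mL twice daily (Section 7.2); 40 subjects (Section 1.1), allocated 1:1 (Section 11.2.1). The last dose of each cream is assumed to fall at the visit that ends its period.

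**The plan's own figure.** Last dose to final visit: 35 − 28 = 7 days, which matches the synopsis. The supply agrees with the period length: 28 mL ÷ 2 mL per day = 14 days.

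**Draws on cream.** Scheduled draws are at Days -7 and 35. Number between Day 0 and Day 28: 0.

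**Last CBD dose to the only post-baseline draw.**

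| Sequence | Nominal | Shortest | Longest |
|---|---|---|---|
| Control, then CBD | 35 − 28 = 7 days | 34 − 29 = 5 | 36 − 27 = 9 |
| CBD, then control | 35 − 14 = 21 days | 34 − 15 = 19 | 36 − 13 = 23 |

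At 1:1 allocation about half the subjects fall in each row. In the second row the draw follows two weeks of control cream and one week of no cream.

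**Interval between the two draws.** 35 − (−7) = 42 days, or 41 to 43 with the Day 35 window. CBD is used on 14 of these, 14/42 = 33%. If the screening sample is taken just before Day 0 and the last draw is on Day 34, the share is 14/34 = 41%.

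**Number of post-baseline draws if all 40 subjects complete.**

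- As scheduled: 1 × 40 = 40.
- Weekly as in Section 4 (Days 7, 14, 21, 28, 35): 5 × 40 = 200, which is 160 more.
- Days 14, 28 and 35: 3 × 40 = 120, which is 80 more.

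**The case against.** The strongest reply is that this is loose drafting in a table for a secondary objective. The two sections that staff work from agree with each other. The frequency labels in the tables err in the other direction too: Section 4 gives the suicidality scale only at baseline and follow-up, yet it is done at every visit. Exposure is modest, about 12.4 mg of CBD per day on the skin, against 67 mg twice daily and 250 mg up to four times daily in the two human trials that the protocol cites as free of adverse events. Eligibility excludes severe liver or renal disease and ALT/AST above 3 times the upper limit of normal. For-cause tests are not barred, and Section 9.2 has vital signs, suicidality and sedation checked weekly and skin at every visit.

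These points bear on severity, and some of them stand. They may justify fewer draws, but the endpoint would then have to say so. None of the weekly checks measures counts, chemistry or liver enzymes, and for-cause tests depend on symptoms.

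Three stronger readings are tempting, and the documents do not support them.

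- **That the schedule contradicts the adverse-event rules.** Section 10.1.3.2 looks at whether an event, "including an abnormal laboratory test result, occurs in a plausible time relationship to study intervention administration", and Section 10.1.4 says "Information to be collected includes event description, time of onset". The first grades relation to study intervention, not to CBD against control, and has a category for uncertain cases. The second lists an item to record. Sparse draws limit what can be entered under either, but conflict with neither.
- **That a planned CBD-versus-control laboratory comparison is lost.** Section 11.2.2 plans none. It is true that both sequences have had CBD by Day 35, but this only limits what may be claimed.
- **That Section 8.3 certainly removes early stoppers from Day 35 and contradicts the safety sections generally.** Section 8.1 also sends trial closure to Section 8.3, so its sentence on further visits is ambiguous. Care on an event (5.1), follow-up of events (10.1.4) and the safety population (11.2.2) can all coexist with it. The real tension is with Section 8.2, the synopsis visit 7 days after the last dose, and the draw for every subject in Section 9.2.

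**Conclusion.** The mismatch is real in the current text and should be fixed. Following Section 9.2 and the schedule cannot deliver the weekly laboratory endpoints of Section 4, or the weekly metabolic and hepatic endpoints of the synopsis. What remains is an uncontrolled check for change that persists one week after the second cream, with 1 post-baseline draw per subject where Section 4 implies 5.

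This does not make the trial's safety monitoring absent, and it leaves the efficacy endpoints untouched. Because rewording alone could reconcile the sections, it ranks below a defect that must be repaired before the trial can proceed.

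The gaps assume on-schedule dosing to the end of each period. How many transient abnormalities would be missed cannot be estimated, since the documents give neither their frequency nor their duration. The early-stopper point is secondary and conditional on how Section 8.3 is read.

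**What to change.** **Preferred.** Add the Section 4 panels at visits that already exist: at minimum Day 14, before the second cream is dispensed, and Day 28, keeping Day 35. Cost: 2 extra draws per subject, 80 in total. Full weekly testing would cost 4 extra per subject, 160 in total. With no washout, Day 14 gives the cleanest look at CBD against control, but with about 20 subjects on each it should be reported descriptively. Day 28 results may carry effects from the first period.

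**If no draws are added.** Restate the endpoint in Sections 1.1 and 4 as laboratory status off treatment, baseline to Day 35, and make no on-treatment or CBD-versus-control laboratory claim. Cost: wording, and a narrower safety conclusion.

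**In either case.** Amend Section 8.3 so that a subject who stops cream without withdrawing consent keeps the visit 7 days after the last dose, with the laboratory draw. Cost: one visit and one draw per early stopper.

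**Clean-up.** Use one blood-count frequency in Sections 1.1 and 4, and have schedule footnote 3 refer to the full Section 9.2 panels, since it now names only some of the tests.
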